5.4 Randomization Criteria

Subject may be randomized anytime (but no later than 12 weeks) during the Run-in Phase when they meet all of the following criteria:

1. Current MRA dose is at least the target dose* (e.g., spironolactone 50 mg/day, eplerenone 50 mg/day) and has been stable for at least 1 week.
2. Current ACEi/ARB/ARNi is $\geq 50\%$ of the target dose* and has been stable for at least 1 week.
3. Current patiromer dose is at least 1 packet daily.
4. Current local serum K^+ level is $\geq 4.0 - \leq 5.0$ mEq/L.

* Study-specific target doses as per Table 4 in the Study Manual.

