1.5 Sample Size

The sample size of 410 subjects per treatment arm (total of 820 subjects) has been calculated to provide 90% power to detect a difference between the control group (placebo) and the active group (patiromer) in change in K^+ levels from Baseline. This sample size calculation is based upon the following assumptions: alpha level of 5% (2-sided); difference between group means of 0.116; a SD of 0.5; and 5% loss to follow-up.

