2.8 Prior/Concomitant Medications and Procedures

All prior and concomitant medications including heart failure and RAASi drugs will be coded using the current version of the World Health Organization Drug dictionary (WHO Drug Global B3 March 2019). Prior and concomitant medications, including heart failure and RAASi drugs, will be separately summarized in the SS. Counts and percentages of subjects using each medication will be computed and summarized by treatment group.

Prior medications are medications with start date before the date of first dose of patiromer in the Run-in phase.

Summaries of concomitant medications will be provided separately for the Run-in and Double-Blinded Treatment Phases.

Concomitant medications during the Run-in Phase are medications with a start date on or before the end of the Run-in Phase and a stop date on or after the first patiromer dose date in the Run-in Phase, or no stop date at all. For subjects who were in the Run-in Phase twice, data from the second Run-in will be summarized. Data from the first Run-in will be included in listings only.

Concomitant medications in the Double-Blinded Treatment Phase are medications with a stop date on or after the first date of treatment in the Randomized Treatment Phase, or no stop date at all. Additional summaries may be provided for concomitant medications of interest.

Summaries of the percent of subjects at 100% and 50% of the target dose for ACEi, ARB, ARNi, MRA and beta blockers will be provided at Baseline, Day 3, and Weeks 1, 2, 6, and 18 for the Safety Set, by treatment group.

Listings of all prior and concomitant medications will be provided.

Listings of concomitant procedures will be presented.

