- Investigator reported AEs of hyperkalemia (first and recurrent) are analysed using a negative binomial regression with the logarithm of the individual follow-up time as offset. The treatment difference will be reported as rate ratio (RR) with 95% CI and p-value from a Wald-type test considering the null hypothesis that the RR is equal to 1. A joint frailty model of the total (first and recurrent) hyperkalemia events and time to death as terminating event may be implemented. If all-cause mortality is substantial in number and differential between the treatment groups, then the joint frailty model would become the main analysis approach.
- Hyperkalemia-related hard outcomes are analysed using the un-matched Win Ratio approach with the following hierarchical components (all assessed during comparable follow-up times):
 1. Time to CV death
 2. Total number of CV hospitalizations
 3. Total number of hyperkalemia toxicity events with serum K+ >6.5 mEq/L
 4. Total number of hyperkalemia events with serum K+ $>6.0-6.5$ mEq/L
 5. Total number of hyperkalemia events with serum K+ $>5.0-6.0$ mEq/L

A death with cause classified as “undetermined” by the event adjudication committee will be considered as a CV death.

- RAASi Use Score will be analysed using the Win Ratio approach for each pair of patients at the end of the comparable follow-up period that is appropriate for that pair of patients, based on the following additive components. Points are accumulated from two components at the respective time for each patient in each comparison:

Component A:

- If during the follow-up (to the respective end of follow-up in the comparator subject) there was a death, the subject is assigned 0 points

- If during the follow-up (to the respective end of follow-up in the comparison) there was a CV hospitalization, but the subject is alive at the end of that follow-up, the subject is assigned 1 point
- If during the follow-up (to the respective end of follow-up in the comparison) there was no CV hospitalization and the subject is alive at the end of that follow-up, the subject is assigned 2 points

Component B:

Further points are collected for the treatment status at the respective end of follow-up in the comparison:

- For ACEi/ARB/ARNi use: >50% of the target dose = 2 points
- For ACEi/ARB/ARNi use: >0 and up to 50% of the target dose = 1 point
- For MRA use: >50% of the target dose = 2 points
- For MRA use: >0 and up to 50% of the target dose = 1 point

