- For beta-blocker use: >50% of the target dose = 2 points
- For beta-blocker use: >0 and up to 50% of the target dose = 1 point

In summary, each subject in each comparison can have 0-8 points (sum of Components A and B) and all subjects are compared using this score at the respective appropriate follow-up time point.

Regression analyses will be adjusted for geographic region as the stratification factor of the randomization and relevant baseline characteristics of the subjects.

For analyses based upon the negative binomial distribution, the subject level count data will be modelled as a function of treatment with the natural log of the subject level follow-up time taken into account in the estimation of the event rate.

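### The RAASi Use Score win ratio takes no account of the Day 1 score, so doses set before randomization decide some pairs and the test loses power, without bias

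*SAP*

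**What the plan says.** SAP 2.10.2 defines the RAASi Use Score as the sum of two components. Component A gives 0 points for death, 1 for a CV hospitalization in a survivor and 2 for neither. For Component B, "Further points are collected for the treatment status at the respective end of follow-up in the comparison". Each of ACEi/ARB/ARNi, MRA and beta-blocker earns 2 points above 50% of target, 1 point for any dose up to 50%, and otherwise none; for example, "For beta-blocker use: >50% of the target dose = 2 points". Then "all subjects are compared using this score at the respective appropriate follow-up time point". Protocol 12.8.2 gives the same scoring.

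The entry rules fix the possible Day 1 values. Protocol 5.4 requires the MRA at target or above, and an ACEi/ARB/ARNi at half of target or more; each dose must be at its required share "of the target dose* and has been stable for at least 1 week". Protocol 5.2, criterion 5, accepts any beta-blocker dose, or none with documented intolerance.

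The only adjustment sentence in SAP 2.10.2 reads: "Regression analyses will be adjusted for geographic region as the stratification factor of the randomization and relevant baseline characteristics of the subjects". A win ratio is not a regression, and no stratification or matching is given for this score. SAP 1.3 stratifies randomization by region only. The Day 1 doses are available: under SAP 2.8 the percentages of "subjects at 100% and 50% of the target dose for ACEi, ARB, ARNi, MRA and beta blockers will be provided at Baseline".

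**The concern.** The score reads absolute dose at the end of follow-up, while subjects start from different places. Two people who change nothing after Day 1 can still be scored as a win and a loss.

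Take a patiromer subject who enters on exactly half the ARB target and no beta-blocker, keeps every dose and has no event. The final score is 2 (Component A) + 1 + 2 + 0 = 5. A placebo subject who enters above 50% of target on all three classes and then loses the MRA completely scores 2 + 2 + 0 + 2 = 6, and wins.

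Such pairs fall in both directions, so they do not favour either arm. They act as noise in the comparison, moving the win ratio toward 1 and making a real effect harder to detect. At stake is the chance of passing the fifth and last step of the fixed sequence.

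**Working it through.** **The plan's own figure.** SAP 1.5 states "The sample size of 410 subjects per treatment arm (total of 820 subjects) has been calculated to provide 90% power", under "alpha level of 5% (2-sided); difference between group means of 0.116; a SD of 0.5; and 5% loss to follow-up". n per arm = 2 × (0.5/0.116)² × (1.960 + 1.282)² = 390.4, so 391; 391/0.95 = 411.6, so 412. The stated 410 is reproduced to within rounding. It concerns the primary endpoint. No effect size or power is stated for the RAASi Use Score.

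**Day 1 spread, from the documents.**

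| Item | Points possible on Day 1 |
|---|---|
| Component A | 2 |
| MRA | 2 |
| ACEi/ARB/ARNi | 1 (exactly 50%) or 2 |
| Beta-blocker | 0, 1 or 2 |

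Component B therefore runs from 2+1+0 = 3 to 2+2+2 = 6. All of the spread comes from two drug classes whose doses were set before randomization.

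**Pairs already unequal on Day 1.** The share is 1 − Σp², where p is the proportion at each score. The dose mix is an assumption. With half of subjects above 50% for ACEi/ARB/ARNi, and beta-blocker points 0/1/2 in 4/46/50%:

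- p(3) = 0.5×0.04 = 0.02
- p(4) = 0.5×0.46 + 0.5×0.04 = 0.25
- p(5) = 0.5×0.50 + 0.5×0.46 = 0.48
- p(6) = 0.5×0.50 = 0.25
- Share = 1 − (0.0004 + 0.0625 + 0.2304 + 0.0625) = 64%

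Over a wide range of mixes the share is 32-65%. If 99% of subjects are in the top category for both classes it is 1 − (0.9801² + 0.0198² + 0.0001²) = 4%.

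**Effect on the test.** I enumerated the score exactly for 410 per arm with that mix. Further assumptions:

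- MRA points lost in 23% (placebo) against 15% (patiromer), half falling to 1 point and half to 0.
- ACEi/ARB/ARNi reduced by one point in 8% against 6%.
- CV hospitalization 10% and death 3% in both arms; beta-blocker unchanged.
- A subject who dies keeps the Component B points.

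Win ratio = W/L, where W and L are the probabilities that a cross-arm pair is won or lost by patiromer. Power = Φ(z − 1.96), where z = (W − L)/SE.

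| | As written | Stratified by Day 1 score |
|---|---|---|
| W, L | 0.402, 0.336 | 0.301, 0.216 |
| Win ratio | 1.20 | 1.39 |
| Ties, 1 − W − L | 26% | 48% |
| z | 1.70 | 2.50 |
| Power | Φ(−0.26) = 40% | Φ(0.54) = 71% |

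As written, 37% of decided pairs involve two subjects who changed nothing. Within strata no such pair is decided.

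**Sensitivity to the assumptions.**

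- If 30% of those entering at 50% of ACEi/ARB/ARNi target are up-titrated in both arms, the win ratio is 1.20 as written and 1.30 stratified; power is 40% and 60%.
- With MRA loss varied from 20% against 13% to 25% against 17%, and dose mixes of 50-70% for ACEi/ARB/ARNi and 35-70% for beta-blocker, the win ratio stays at 1.17-1.22 as written and 1.27-1.40 stratified. Power is 33-44% and 52-71%; the lowest stratified values combine the smallest effect with up-titration.
- A separate enumeration assumed a larger effect: MRA loss 25% against 14%, ACEi/ARB/ARNi reduction 8% against 5%, CV hospitalization 8% and death 2% in both arms. It gave a win ratio of 1.29 as written and 1.57 stratified. Power was 67% for the absolute score and 94% for change from Day 1. With 99% of subjects in the top dose category, the win ratios were 1.57 and 1.59.
- With identical arms the win ratio is 1.00.

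These powers are for the test taken alone. Under the fixed sequence it is reached only if the earlier steps succeed.

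**The case against.** The strongest reply is that the score is meant as a status measure. Protocol 3.3 and 12.8.2 define it as death, CV hospitalization, and use and dose of three drug classes, beta-blocker included. Preservation of RAASi treatment is measured directly elsewhere: by key secondary 2, where everyone starts at the MRA target, and by the enablement and discontinuation endpoints in SAP 2.9. This stands. It rules out rescoring, but it does not explain why known Day 1 differences should go unadjusted in a comparison of that status.

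A reader might infer several stronger claims that the documents do not support:

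- *That all the background doses are fixed at randomization.* Protocol 4.1 asks for up-titration to be attempted below target when potassium is in range, and Protocol 6.7.1.2 allows down-titration for hyperkalemia. ACEi/ARB/ARNi points can therefore carry some treatment effect. Only the beta-blocker item looks largely static (Protocol 6.8.4).
- *That Day 1 differences add ties.* They break ties at random: 26% as written against 48% stratified above.
- *That the result is biased, or understates preservation of therapy.* Randomization balances Day 1 doses on average, and the endpoint is not defined as preservation.
- *That the loss of power is established.* No dose mix or rate of dose loss is given. Protocol 6.7.2 aims at full target doses during Run-in, which could compress the ACEi/ARB/ARNi spread.

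**Conclusion.** The point holds as a loss of efficiency. The absolute score, the permitted Day 1 range of 3 to 6 and the absence of any baseline adjustment for this win ratio all follow from the documents. Attenuation toward 1 appeared in every non-null scenario with any Day 1 spread.

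The size is illustrative. It is about 1.2 against 1.3-1.4 on the win ratio, and roughly 30-45% against 55-75% in power, for modest effects and a mixed Day 1 dose distribution. It shrinks when ACEi/ARB/ARNi up-titration is common, and is negligible if nearly everyone enters in the top category. Type I error is unaffected. Because this is the last key secondary test, no later confirmatory test depends on it. The change is worthwhile because it is cheap, but the plan is valid without it.

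**What to change.** Before unblinding, add to SAP 2.10.2:

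- Keep the 0-8 score exactly as defined, including the beta-blocker item.
- Form win-ratio pairs only within strata of the Day 1 Component B score (3, 4, 5, 6). State a rule for merging 3 with 4 if sparse; in the mix above, stratum 3 would hold about 0.02 × 410 = 8 subjects per arm.
- Prespecify the weights, for example win ratio = Σ(wins in stratum / stratum size) ÷ Σ(losses in stratum / stratum size), with the matching variance.
- Report the unstratified win ratio as a sensitivity analysis, with the share of decided pairs in which neither subject changed after Day 1.

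Do not replace the score with change from Day 1, or drop the beta-blocker item, in the main analysis. Either would redefine an endpoint set in Protocol 3.3 and 12.8.2. A change score would also let a subject entering at 50% gain a point that one at full dose cannot.

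The cost is a paragraph of SAP text and a small amount of programming, using Day 1 doses that the trial already records. The analysis becomes slightly more complex, more pairs tie, and the sparsest stratum contributes little. SAP 3 treats database lock as still to come and SAP 1.4 keeps the sponsor blinded, so the change can be made on pre-randomization data alone.

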2.10.3 Other Secondary Endpoint Analyses

The additional endpoints listed below (Other Secondary Endpoints) will be summarized by treatment arm. When treatment comparisons are made, 95% CI and unadjusted p-values will be presented in the FAS set.

For each of these additional secondary endpoints, the analysis will be conducted using only data through June 24, 2021. Endpoints originally planned to be assessed at the EoS visit will instead be assessed using the last available data on or before June 24, 2021.

- Durable enablement to stay on the target dose of ACE/ARB/ARNi [REDACTED]
[REDACTED]
Note: Discontinuation of the target dose for at least 14 days (or less if at the EoS) is required to confirm this endpoint
- Durable hyperkalemia-free enablement to stay on the MRA target dose (days on 50 mg MRA without presence of hyperkalemia) [REDACTED]
- Hyperkalemia toxicity events with serum $K^+ > 6.5$ mEq/L [REDACTED]
- Hyperkalemia events with serum $K^+ > 6.0-6.5$ mEq/L [REDACTED]

- Emergency treatment for hyperkalemia (hospitalization or emergency room) [REDACTED]
[REDACTED]
- Total number of hyperkalemia events with serum $K^+ > 5.0-6.0$ mEq/L [REDACTED]
[REDACTED]
- Investigator reported events of hyperkalemia (time to first event) [REDACTED].
- Proportion of subjects on $\ge 50\%$ of target dose of ACEi, ARB, or ARNi and $\ge 50\%$ of target dose of MRA at the EoS Visit [REDACTED]
[REDACTED]
- Time to first occurrence of CV death or CV hospitalization [REDACTED]
[REDACTED]
- Time to MRA discontinuation, [REDACTED]
[REDACTED]
[REDACTED]
- Time to first occurrence of MRA discontinuation or death, [REDACTED]
[REDACTED]
- Time to ACEi/ARB/ARNi discontinuation, [REDACTED]
[REDACTED]
[REDACTED]
- Time to first occurrence of ACEi/ARB/ARNi discontinuation or death, [REDACTED]
[REDACTED]

2.10.4 Other Analyses

The analyses listed below will be conducted using only data through June 24, 2021, except for the analysis of high sensitivity troponin. [REDACTED]
[REDACTED]
[REDACTED]

Endpoints originally planned to be assessed at the EoS visit will instead be assessed using the last available data on or before June 24, 2021.

- CV death [REDACTED]
- First and recurrent CV hospitalizations [REDACTED]
[REDACTED]
- First and recurrent HF hospitalizations (or equivalent in outpatient clinic) [REDACTED]
[REDACTED]
- KCCQ questionnaire - OSS, CSS and TSS [REDACTED]
[REDACTED]
[REDACTED]
- Mean change in EQ-5D-5L total score based on a visual analog scale from randomization to each time point measured post-randomization [REDACTED]

- Proportion of subjects on any dose of MRA at the EoS Visit, [REDACTED]
[REDACTED]
- Proportion of subjects on any dose of ACEi, ARB or ARNi at the EoS Visit, [REDACTED]
[REDACTED]
- Mean Change in proteinuria from Day 3 of the Blinded Treatment Phase to the EoS Visit, [REDACTED]
[REDACTED]
- Mean Change in NT-proBNP from screening to each time point measured post-randomization for which at least 10% of subjects have an assessment, [REDACTED]
- Mean Change in high sensitivity troponin from randomization at the EoS Visit, [REDACTED]
[REDACTED]
- Change in Functional status by NYHA class [REDACTED]
[REDACTED]
- 30-day HF re-hospitalization rate after a prior HF hospitalization, [REDACTED]
[REDACTED]
- Mean changes in serum K+ from Baseline to individual visits
- Slope of eGFR change during the study, [REDACTED]

[REDACTED]
[REDACTED]
[REDACTED]
[REDACTED]
[REDACTED]
[REDACTED]
[REDACTED]
[REDACTED]
[REDACTED].

2.11 Analyses of Data in the Run-in Period

The analyses described in this section will use a modified Run-in Set. Subjects in the Run-in Set who were discontinued prematurely from Run-in during Spring 2020 due to Covid-19 or were discontinued prematurely after study closure was announced on June 24, 2021, will be excluded.

Screening Characteristics

Differences between the modified Run-in and Randomized Sets will be summarized for selected characteristics at Screening.

Predictors of Selected Outcomes During Run-in

Summary statistics will be provided for the following outcomes in Run-in, separately for the Randomized Set and the modified Run-in Phase Set:

- Inability to achieve MRA target dose (stable for at least one week) during Run-in
- Inability to achieve ACEi/ARB/ARNi target dose (stable for at least 1 week) during Run-in

- Inability to achieve at least 50% of the ACEi/ARB/ARNi target dose (stable for at least 1 week) during Run-in
- Hyperkalemia event during Run-in ($K^+ > 5.5$)
- Hypokalemia event during Run-in

For the above outcomes, selected screening characteristics will be assessed as potential predictors. Characteristics to be assessed may include, but are not limited to:

- eGFR < 60;
- NT-proBNP
- Systolic BP
- Ischemic cause of heart failure (Y/N)
- Diabetes Mellitus (Y/N)
- Sex (M/F)
- NYHA (I, II vs. III vs. IV)
- BMI
- Hyperkalemia (Y/N) – as a predictor of inability to reach target dose

RAASi Medication Use

Use and dose level of RAASi heart failure medications will be summarized at the end of the Run-in Period, separately for the modified Run-in Set and the Randomized Set.

KCCQ

Summary statistics will be provided for the FAS for the KCCQ Overall Summary Score at Screening, at Baseline, and for the Change from Screening to Baseline.

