Note: If one screening K^+ value is >5.0 mEq/L and one value is ≤ 5.0 mEq/L, then a third peripheral venipuncture is performed within 1 day to obtain clarity, whether subject is hyperkalemic or normokalemic (local serum $K^+ \geq 4.0 - \leq 5.0$ mEq/L).

All other subjects are considered normokalemic and serum K^+ will be measured again latest after the first week during the Run-in Phase. Patiromer will be started at this first Run-in Visit only if subjects are still normokalemic or have progressed to hyperkalemia; in case of newly observed hypokalemia (local serum $K^+ < 4.0$ mEq/L) during the first Run-in Week, patiromer must not be given. In subjects with hypokalemia serum K^+ must be controlled after 3 days. During the first week of Run-in, ACEi/ARB/ARNi and/or MRA doses ideally remain unchanged, if clinically indicated. On or after the Run-in Week 1 Visit, up-titration of ACEi/ARB/ARNi and/or MRA may be initiated.

Patiromer is titrated during Run-in Phase to achieve target local serum K^+ level of $\geq 4.0 - \leq 5.0$ mEq/L; see Section 6.7.1.1 for patiromer titration algorithm. Note: Depending on the actual local serum K^+ value this could include patiromer 0 g/day (i.e., 0 packets/day) during the Run-in Phase.

Optimization of ACEi/ARB/ARNi or MRA During Run-in Phase:

The Investigator should manage ACEi/ARB/ARNi or MRA dose initiation, escalation and maintenance with the aim to achieve 100% of target doses as per the Study Manual, using clinical judgment to customize ACEi/ARB/ARNi or MRA addition or dose escalation based on subject response; see Section 6.7.2, Section 6.8.2, and Study Manual [1] for a summary of practice guideline recommendations.

Initiation or escalation of ACEi/ARB/ARNi or MRA dose should be made with caution when local serum K^+ is >5.0 mEq/L. Assessment of serum K^+ will occur at each visit. The patiromer dose is titrated based on the subject's K^+ level.

Subjects may be randomized anytime (but no later than 12 weeks) during the Run-in Phase when they meet all of the randomization criteria; see Section 5.4.

Treatment Phase (Double-Blinded):

After the Run-in Phase (single-blinded), eligible subjects will be randomized in a 1:1 ratio, to treatment with patiromer or placebo double-blinded; see Study Schema.

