2 STATISTICAL METHODOLOGY AND STATISTICAL ANALYSES

2.1 Populations Analysed

Four analysis populations will be defined.

2.1.1 *Randomized Set*

All subjects randomized to study treatment.

2.1.2 *Full Analysis Set*

The full analysis set (FAS) consist of all subjects who satisfy the following criteria:

- Randomized to treatment
- Received at least 1 dose of randomized treatment

The full analysis set will be the primary population used for the evaluation of efficacy.

2.1.3 *Safety Set*

The safety set (SS) consists of all randomized subjects who have taken at least 1 dose of randomized study medication. The subjects in this group will be analysed based on the treatment they received, with data summarized separately for the Run-in and Double-Blinded Treatment Phases of the study.

2.1.4 *Run-in Phase Set*

The Run-in Phase Set will consist of subjects who signed informed consent and received patiromer during the Run-in Phase but were not randomized. This set will be used to summarize safety related events that may be related to patiromer treatment.

At the beginning of the Covid-19 pandemic, in order to ensure subject safety, all subjects who were in the Run-in Phase were discontinued. These subjects were given the opportunity to be re-screened once Covid-19 restrictions were eased in their respective locations. Those who were still eligible were entered into the Run-in Phase again.

Details for handling the adverse event, laboratory and concomitant medication data for subjects with two separate periods of Run-in Phase are provided in the appropriate sections below.

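### The COVID-19 exclusion in SAP 2.11 is tied to the subject, not to the interrupted Run-in, so re-entrants who genuinely failed are dropped while re-entrants who were randomized are kept

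*SAP*

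**What the plan says.** The parent set is defined in SAP 2.1.4: "The Run-in Phase Set will consist of subjects who signed informed consent and received patiromer during the Run-in Phase but were not randomized". A subject who is eventually randomized is therefore never in it.

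The same section reports that everyone in Run-in when the pandemic began was stopped and could be re-screened later: "Those who were still eligible were entered into the Run-in Phase again". Some subjects thus have two Run-in periods.

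SAP 2.11 derives a modified set by removing "Subjects in the Run-in Set who were discontinued prematurely from Run-in during Spring 2020 due to Covid-19 or were discontinued prematurely" once closure had been announced. The full closure clause reads "discontinued prematurely after study closure was announced on June 24, 2021, will be excluded". Screening characteristics and Run-in outcomes (inability to reach dose, hyperkalemia, hypokalemia) are then set beside those of the Randomized Set, to which no matching exclusion applies.

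Elsewhere the SAP does say how to treat two periods. SAP 2.8 states: "For subjects who were in the Run-in Phase twice, data from the second Run-in will be summarized". SAP 2.17 repeats this for safety. SAP 2.12.2 takes screening values from the last screening that led into Run-in. SAP 2.11 repeats none of these rules.

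**The concern.** An administrative exclusion should remove Run-in periods that could not run their course. The COVID-19 clause instead marks the subject for good. A subject interrupted in Spring 2020 who came back, had a second Run-in and failed on its merits still meets the wording. A subject with the same history who was randomized cannot meet it, because the clause reaches only the non-randomized set. Who is described then depends partly on the outcome being described.

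This matters most for the dose outcomes. Protocol 5.4 requires the MRA target dose, and at least half the ACEi/ARB/ARNi target dose, before randomization. Two of the three inability outcomes in SAP 2.11 are therefore almost absent from the Randomized Set by design. What the study can say about them comes from the one set that this clause trims. Two programmers could also build different sets from the same text.

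**Working it through.** The plan states no figure for this set, so there is nothing to reproduce. The check traces subjects through the definitions and then illustrates the size on assumed inputs.

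**Paths for a subject dosed in Run-in and stopped in Spring 2020**

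| What happened next | In the Run-in Phase Set (2.1.4)? | 2.11 read literally | Rule based on the last Run-in |
|---|---|---|---|
| Never re-entered | Yes | Excluded (unresolved) | Excluded |
| Re-entered, then failed | Yes | **Excluded** | **Kept, second Run-in** |
| Re-entered, then randomized | No | Exclusion cannot apply; in Randomized Set | Same |
| Re-entered, stopped at closure | Yes | Excluded (unresolved) | Excluded |

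Only the second row differs, and it is the only row with a genuine failure.

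**Illustrative size.** Let f be the true failure share and c the share of resolved entrants who are COVID-19 re-entrants. Both are assumed, and re-entrants are taken to fail at the same rate as others. Failures kept are f(1 − c) and all subjects kept are 1 − fc, so the described failure share is f(1 − c)/(1 − fc). The fraction of genuine failures lost equals c.

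| f | c = 2% | c = 5% | c = 10% | c = 15% |
|---|---|---|---|---|
| 10% | 9.8% | 9.5% | 9.1% | 8.6% |
| 20% | 19.7% | 19.2% | 18.4% | 17.5% |
| 30% | 29.6% | 28.9% | 27.8% | 26.7% |
| 40% | 39.5% | 38.8% | 37.5% | 36.2% |

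Example: 0.20 × 0.90/(1 − 0.02) = 0.18/0.98 = 18.4%. The reduction runs from 0.2 points (10 − 9.8) to 3.8 points (40 − 36.2).

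**Predictors.** If k0 and k1 are the shares of failures kept at the two levels of a predictor, the odds ratio after removal is the true one times k1/k0. With a true value of 2.0:
- k0 = k1 = 0.90 leaves it at 2.0.
- k0 = 0.95, k1 = 0.85 gives 1.79.
- k0 = 0.85, k1 = 0.95 gives 2.24.
- k0 = 0.95, k1 = 0.75 gives 1.58.

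**Closure, for the optional sensitivity summary only.** Assume uniform entry over T weeks, randomization uniform over weeks 2 to 12 (mean 7), and mean failure time m. Successes observed are (1 − f)(1 − 7/T) and failures observed are f(1 − m/T). With f = 20%:
- T = 78, m = 12 (all failures at week 12): 0.1692/(0.1692 + 0.7282) = 18.9%.
- T = 130, m = 9.25 (half at week 12, half spread over weeks 1 to 12, mean 6.5): 0.1858/(0.1858 + 0.7569) = 19.7%.

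The entry date that leaves a full 12 weeks before closure is 24 June 2021 minus 84 days, which is 1 April 2021.

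**The case against.** The strongest reply is that the SAP's general convention already settles the matter. Sections 2.8 and 2.17 let the second Run-in stand for a subject with two, and 2.12.2 uses the last screening. On that footing a re-entrant's Run-in did not end in Spring 2020 and the exclusion does not bite. This is probably what was meant, and it is why the point is minor. But those rules say which data to summarize, not who belongs to the 2.11 set, and 2.1.4 announces them for adverse events, laboratory and concomitant medication data. Followed as written, 2.11 drops these subjects.

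A reader might infer more than the documents support:

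- *That subjects cut off by COVID-19 or by closure are failures being hidden.* They are unresolved. The Synopsis defines Run-in failure as criteria unmet after 12 weeks or one of two potassium rules. Counting interrupted subjects as unable to reach dose would misclassify them, so leaving them out is defensible. It is true that "Subject may be randomized anytime (but no later than 12 weeks) during the Run-in Phase", so near a stop date early successes are kept while slower outcomes are cut off. Trimming the Randomized Set to match is a reasonable refinement, not a correction the plan must make.
- *That Run-in success will be overstated.* SAP 2.11 plans no success rate. Run-in disposition and reasons for non-randomization are in SAP 2.3, and screening characteristics of the unmodified set are in 2.5. The exclusion touches neither.
- *That the predictor analyses are biased.* They shift only if, among failures, removal depends on the predictor. Nothing in the documents shows that it does.
- *That undosed entrants are wrongly missing.* For newly hypokalemic subjects "during the first Run-in Week, patiromer must not be given", so some may be in neither set. But 2.1.4 limits the parent set to dosed subjects for a stated safety purpose, which is coherent, and no number can be put on this group.

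**Conclusion.** The concern holds in a limited form. As written, the COVID-19 clause in SAP 2.11 removes re-entrants who genuinely failed and keeps re-entrants who were randomized, contrary to the SAP's own second-Run-in convention. Its size cannot be derived from the documents. Over assumed re-entry shares of 2% to 15% and failure shares of 10% to 40%, a failure share formed from the two sets would be understated by about 0.2 to 4 points, and 2% to 15% of genuine failures would be missing from the modified set. These figures assume that re-entrants fail at the same rate as other entrants. The affected outputs are supplementary descriptive summaries that SAP 3 lists as additions to the protocol. No primary or key secondary result is affected. Severity: minor.

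**What to change.** Reword the exclusion in SAP 2.11 so that a subject leaves the Run-in Set only if the last Run-in ended because of COVID-19 or the 24 June 2021 closure. State that the second Run-in, with its screening values, represents everyone who re-entered. Subjects whose only or last Run-in was stopped administratively may stay excluded.

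The cost is one sentence and one derivation. A small side effect is that a subject whose first Run-in genuinely failed and whose second was cut off would be excluded. Protocol 8.1.1.1 makes this path possible, and under 2.8 and 2.17 the first-period data remain in listings.

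Optionally, add a sensitivity summary that limits both sets to subjects whose last Run-in began at least 12 weeks before the relevant stop date (for closure, by 1 April 2021). Its cost is that some late-entering randomized subjects leave that comparison.
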